Follow-up appointments at 6 months, 9 months, and 12 months will be completed for subjects. The follow-up appointments will consist of a clinical examination and bite-wing view periapical radiographs to determine success(s)/failure(s) of two different pulpotomized teeth.

The criteria for a successful pulpotomy will include:

- retained for the length of the study or exfoliate naturally
- normal bone trabeculation in the periapical region
- no abscess or fistula
- contained internal resorption is acceptable
- calcific metamorphosis is acceptable

When the teeth exfoliate or require extraction, the teeth with pulpotomies will be collected and histologic slices will be completed to analyze for what types if any cellular changes from the use of the pulpal medicaments.

Statistical Analysis:

Data and statistical analysis will include descriptive and inferential statistics. Inferential statistical analysis will use SPSS 16 (SPSS, Chicago, IL) with a significance level set at $P \leq 0.05$

Budget:

Item	Units Needed	Price/Unit	Total Price
Patient incentive – follow-up visits	60	\$50	\$3000
Mineral Trioxide Aggregate	5 dose packets	\$475	\$475
Ferric Sulfate	1	\$35	\$35
3M Stainless steel crowns	60	\$5	\$300
Copying, stationery , paper, pen, 2 clip board			\$300.00
Total			\$4,110

Proposed Research Milestones:

Continuation of Established IRB#: 5140262

March 2016:

- Data collection

March 2016:

- Proposal preparation and submission for approval by the Research Guidance Committee

April 2016:

- Protocol preparation, submission, and approval by Loma Linda University School of Dentistry Research Committee

June 2016- June 2017:

- Data analysis and article preparation for review and submission

References:

- Casamassimo, P. S. (2013). Pediatric Dentistry Infancy Through Adolescence. St. Louis, Missouri, Elsevier Saunders.
- Chen, J. W. (2012). "Materials for primary tooth pulp treatment: the present and the future." Endodontic Topics 2012 **23**: 41-49.

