Title page:

Title: Comparison of Clinical and Radiographic Success Between:
Mineral Trioxide Aggregate (MTA) & Ferric Sulfate (FS) Pulpotomies for Primary Molars.

NCT 02783911

Date: Sep 02, 2014

Comparison of Mineral Trioxide Aggregate and Ferric Sulfate:
Pulpal Medicaments for Pulpotomized Primary Teeth

Statistical analysis plan

The following clinical information were collected from the charts: Mobility, pain, abscess/draining fistula, and facial swelling. Exfoliation of the pulp treated teeth was recorded and graded as normal, early, or delayed based on the age of the patient at the time of the recall and on the exfoliation status of the contralateral tooth. If there is any clinical signs of the above the tooth will be count as clinical failure.

Data was analyzed using the Statistical Package for Social Sciences v 16.0 (SPSS Inc., Chicago, Ill). The difference between the materials was analyzed using chi-square, Significance level was set $P < .05$.

Chi-Square Tests

	Value	df	Asymptotic Significance (2- sided)	Exact Sig. (2- sided)	Exact Sig. (1- sided)
Pearson Chi-Square	.059 ^a	1	.808		
Continuity Correction ^b	.000	1	1.000		
Likelihood Ratio	.060	1	.807		
Fisher's Exact Test				1.000	.603
Linear-by-Linear Association	.057	1	.812		
N of Valid Cases	24				

a. 2 cells (50.0%) have expected count less than 5. The minimum expected count is 2.25.

b. Computed only for a 2x2 table

Summary: The result showed there is no statistical difference in long term clinical success between the two pulpotomy medicaments. (MTA vs FS)

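### The protocol aims to compare radiographic as well as clinical success, but the SAP defines only clinical failure, concludes only on clinical success and contains no radiographic analysis

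*Protocol*

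**What the plan says.** **Protocol.** The title and the Statement of Problem commit the study to comparing success on both clinical and radiographic grounds. Methods and Materials schedules visits at 6, 9 and 12 months, each with a clinical examination and films, and uses both to decide success or failure. The list opens with "The criteria for a successful pulpotomy will include" and has five items: retention or natural exfoliation, "normal bone trabeculation in the periapical region", absence of abscess or fistula, and two tolerated findings (contained internal resorption and calcific metamorphosis). The Statistical Analysis section gives the software and the significance level but names no outcome and no test.

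**SAP.** The title page repeats "Comparison of Clinical and Radiographic Success Between". The data items are clinical: "The following clinical information were collected from the charts: Mobility, pain, abscess/draining fistula, and facial swelling". It adds "Exfoliation of the pulp treated teeth was recorded and graded as normal, early, or delayed". The only failure rule is "If there is any clinical signs of the above the tooth will be count as clinical failure". One chi-square table follows, with 24 valid cases and no row, column or outcome labels. The summary states that "there is no statistical difference in long term clinical success between the two pulpotomy medicaments".

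**The concern.** A radiographic comparison is half of the stated aim, and the protocol collects films for that purpose. The SAP is the only document that says how outcomes are scored and compared, and it never mentions a film. Even the periapical criterion that the protocol does spell out has no counterpart there.

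Two things are at stake. The two documents can classify the same tooth differently. And someone who follows the SAP exactly will finish without an answer to the radiographic question, with nothing in the text to say that the question was set aside.

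**Working it through.** **1. The SAP's own figures.** N = 24, and the table footnote says "The minimum expected count is 2.25". The minimum expected count is (smaller row total × smaller column total) / N, so the product is 2.25 × 24 = 54. With both totals at most 12, the only integer pair is 6 and 9, giving margins 6/18 and 9/15. Seven tables have these margins, and only [[2, 4], [7, 11]] (or its transpose) matches the printout:

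- Pearson = N(ad − bc)² / (product of the four margins) = 24 × (2×11 − 4×7)² / (6×18×9×15) = 24 × 36 / 14,580 = 0.0593, p = 0.808 (printed .059, .808).
- Continuity-corrected: |ad − bc| − N/2 = 6 − 12 is negative, so it is set to 0, p = 1.000 (printed .000, 1.000).
- Likelihood ratio 0.0599, p = 0.807 (printed .060, .807).
- Linear-by-linear = 0.0593 × 23/24 = 0.0568, p = 0.812 (printed .057, .812).
- Fisher 1.000 two-sided, 0.603 one-sided (as printed).
- Expected counts 2.25, 3.75, 6.75 and 11.25, so two are below 5 (as printed).

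The printout is internally consistent. It describes one binary outcome in 24 cases. It does not show which margin is the treatment, which level is failure, or what the outcome is. The outcome is taken to be clinical failure because that is the only failure the SAP defines and because the summary refers to clinical success. The reconstruction does not measure the size of the gap; it shows only that one outcome was tabulated.

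**2. The documents side by side.**

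| Element | Protocol | SAP |
|---|---|---|
| Aim or conclusion | clinical and radiographic success | conclusion on clinical success only |
| Data | examination and films at 6, 9, 12 months | clinical signs from charts, exfoliation grade |
| Radiographic criterion | normal periapical bone; two tolerated findings | none |
| Failure rule | failure to meet the success criteria | clinical signs only |
| Radiographic tests or results | not specified | 0 |

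**3. One tooth under both rules.** Take a retained tooth with no mobility, pain, abscess, fistula or swelling, but with abnormal periapical bone at 12 months. Under the protocol it misses a listed criterion and is not a success. Under the SAP it shows no listed clinical sign and is not a failure. This holds however broadly the success list is read, because the periapical item is explicit.

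**4. Minor note on the list.** Eligibility in Methods and Materials excludes teeth with furcation radiolucency, inter-radicular bone destruction or external root resorption, and treats physiologic resorption separately. The post-procedure film must show the furcation and the whole root. The success list names neither furcation/inter-radicular bone nor external resorption. Baseline imaging of the area is therefore required, but the scoring of new lesions there is left to the examiner.

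**5. What cannot be computed.** No radiographic count, by arm or overall, appears in either document. No corrected success rate, difference or p-value can be derived.

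**The case against.** The strongest reply is that the SAP claims no more than it analyses. Its summary is confined to clinical success, no radiographic rate is reported, and its inner heading speaks only of comparing the two materials as pulpal medicaments. The radiographic wording sits on a title page that repeats the protocol's title. This stands as far as it goes: the clinical conclusion is not made wrong by the omission, and the SAP title alone would be thin evidence. The protocol's stated aim and its film schedule are the firmer basis, and the reply does not meet them.

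A second reply concerns the success list. Its opening makes it open-ended, and naming two changes as tolerated suggests that others are not. The retention item and the SAP's exfoliation grade may also catch some progressive resorption; the SAP failure rule follows the exfoliation sentence, so early or delayed exfoliation may count as failure. All of this stands, which is why the list is only a clarity point. A reader might infer that the protocol would pass furcation lesions or external resorption as successes. That treats an open list as closed, and the text does not support it.

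Third, the table is unlabelled, so it is not stated that clinical failure was tested. That also stands. The inference is well supported but remains an inference.

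**Conclusion.** The point holds as an inconsistency between protocol and SAP: a planned outcome, with films scheduled to measure it, has no definition, analysis or result in the SAP. Its size is zero radiographic analyses against one unlabelled 2×2 table of 24 cases. The one assumption is that this table concerns clinical failure. If it did not, the SAP would have tested an outcome that it nowhere defines.

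Stronger readings are tempting. A reader might infer that success is overstated, that one material is favoured, or that scoring the films would overturn the finding of no difference. No radiographic rate is reported that could be overstated, clinically silent lesions do not alter a clinical-only result, and nothing in the documents gives the number of such lesions or their split by arm. Nor do the documents say why the radiographic comparison is absent, so selective reporting cannot be concluded. What follows is narrower: the radiographic question is unanswered, and the sponsor should either answer it or say openly that it was not analysed.

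**What to change.** Add to the SAP, by arm, radiographic success and overall success (clinical and radiographic together), using the protocol's criteria and the films already scheduled.

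- **Definition.** State that new furcation or inter-radicular radiolucency, and external root resorption that is not physiologic, count as radiographic failure when judged against the post-procedure film. Keep the periapical criterion and both tolerated findings.
- **Time point.** Take 12 months as the main one: it is the last scheduled visit and matches the retention period required at entry. Show 6 and 9 months beside it.
- **Exfoliation.** Say how naturally exfoliated teeth are counted. The protocol list treats natural exfoliation as compatible with success; the SAP should say whether an earlier failed film overrides this.
- **Missing data.** Report missing and unreadable films by arm and visit.
- **Reading.** Have films read without sight of the allocation list or the clinical outcome. Note that masking may be imperfect: the protocol's literature review lists radiopacity among the properties of MTA, so the material may be visible.
- **Labelling.** Label the chi-square table with its outcome and arms. Because a result is already reported, mark both the added definitions and any re-scoring as post hoc.

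If the films cannot be scored, state that radiographic success was planned but not analysed, and keep the conclusion to clinical success. Retitling alone would hide a planned outcome.

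**Cost.** No added visits. For the 24 analysed cases, assuming one film per case per visit, the reading load is at most 24 × 3 = 72 follow-up films plus 24 post-procedure films, 96 in all. The documents do not show that every film can be retrieved, so the usable number may be lower. The downside is reader time and success rates that may come out lower.

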Title page:

Title: Comparison of Clinical and Radiographic Success Between:
Mineral Trioxide Aggregate (MTA) & Ferric Sulfate (FS) Pulpotomies for Primary
Molars.

NCT 02783911

Date: Sep 02, 2014

Statement of Problem

Premature loss of a tooth from caries or trauma can lead to malocclusion and/or to esthetic, phonetic, function problems, super eruption of the opposing tooth and costly procedures to correct and maintain space. A pulpotomy is one type of treatment for vital pulp therapy. The aim of the treatment is to preserve the radicular pulp, avoiding pain and swelling, to retain the tooth and preserve arch integrity.

Formocresol (FC) has a long history for pulpal medicament with a success rate of up to 97%. Its use, however, has been questioned due to published studies raising concerns for systemic distribution, carcinogenicity, mutagenicity, and immune sensitization. These concerns have led to the search and use of different materials and techniques to replace FC as a pulpal medicament that is cost effective, safe, and predictable. Calcium hydroxide, diluted formocresol, electrosurgery, lasers, ferric sulfate (FS), mineral trioxide aggregate (MTA), and sodium hypochlorite have been used as alternatives to FC for pulp therapy. Of these alternatives, MTA and FS have the most similar clinical and radiographic success as FC but the number of studies evaluating their success is limited in primary teeth. There has not been any study comparing MTA to FS for use in primary molar pulpotomies.

The purpose of this study is to evaluate which of these materials, gray MTA (GMTA) or FS, has the best long-term success rates with the least amount of adverse effects in primary molar pulpotomies. We will clinically and radiographically compare the success rates of MTA and ferric sulfate pulpotomies in primary teeth.

Review of Literature

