- 9) MTA is a biocompatible material and its sealing ability is better than that of amalgam or zinc oxide-eugenol. It is a powder that sets in the presence of moisture with a pH of 12.5. The setting time of the cement is 4 hours and its compressive strength is 70 MPA, which is comparable with that of IRM (Torabinejad, M., 1999).

Methods and Materials

Children between the ages of 4-9, with first or second primary molars with normal or reversible pulpitis that have vital carious pulp exposures due to caries and pulps that bleed when entering the pulp chamber. No clinical symptoms or evidence of pulp degeneration, such as excessive bleeding from the root canal, history of swelling, mobility, or sinus tract. No radiographic signs of internal or external root resorption, inter-radicular and/or periapical bone destruction, or furcation radiolucency. No more than one third physiologic root resorption has occurred. Teeth that will be retained for 12 months after the pulpotomy procedure and stainless steel crown restoration, will be asked to participate in this study. Children can be ASA I or II that have cooperative behavior that will enable follow-up appointments for examinations and radiographs. Children meeting the criteria for this study will be treated at Loma Linda University's Pediatric Dental Clinic, LLU Children's Hospital with general anesthesia, or Koppel Special Care Dentistry Center at LLU.

Prior to pulpotomy treatment, the subjects will be randomly assigned into two groups: 1) MTA pulpotomy with stainless steel crown or 2) ferric sulfate with stainless steel crown. Operators involved will draw blindly into a box that has 60 papers: 30 marked MTA and 30 marked FS. The teeth will be anesthetized using 2% lidocaine with (1:100Kepi). The tooth will be isolated using a rubber dam. A new slow-speed #6 or #8 round bur will be used to remove caries. A new #330 carbide bur and a high speed will be used to access pulp chamber. Hemostasis will be achieved with direct pressure from a sterile cotton pellet moistened with sterile water. MTA or FS (whichever randomly assigned) will be placed onto pulpal stumps. ZOE B&T mixture will be placed into pulp

chambers. Molar will be immediately restored with a stainless steel crown cemented with Ketac-Cem Liquid. A post procedure bitewing radiograph, that shows the subject's tooth furcation and complete root, will be taken.

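### The protocol's success list and the SAP's clinical failure rule use different signs, so the same tooth can be a success under one document and a failure under the other.

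*Protocol*

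**What the plan says.** The protocol (Methods and Materials) has each follow-up visit combine a clinical examination with radiographs to decide success or failure. The list is introduced by "The criteria for a successful pulpotomy will include" and sets three requirements: "retained for the length of the study or exfoliate naturally", "normal bone trabeculation in the periapical region" and "no abscess or fistula". It then accepts two findings, contained internal resorption and calcific metamorphosis.

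The SAP (Statistical analysis plan) says that these signs were taken from the charts: "Mobility, pain, abscess/draining fistula, and facial swelling". Exfoliation was also graded as normal, early or delayed. The rule follows: "If there is any clinical signs of the above the tooth will be count as clinical failure". The SAP states no radiographic criterion, and its summary speaks of clinical success only.

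Elsewhere in the protocol the three other signs appear only outside the outcome definition. The Statement of Problem says: "The aim of the treatment is to preserve the radicular pulp, avoiding pain and swelling, to retain the tooth and preserve arch integrity". The entry criteria exclude teeth with "history of swelling, mobility, or sinus tract".

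**The concern.** Each document gives a rule for sorting teeth into successes and failures, and the rules disagree in both directions. Of the SAP's four signs, only abscess or fistula is on the protocol list. Of the protocol's three requirements, the bone criterion has no counterpart in the SAP.

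The outcome prespecified in the protocol is therefore not the outcome analysed. The failure rate for each material, and which material looks better, may depend on which document is followed. With 24 teeth analysed, a change in one or two of them is visible in the result.

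**Working it through.** **1. The two rules side by side**

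| Finding in a treated tooth | Protocol list | SAP clinical rule |
|---|---|---|
| Abscess or fistula | fails | fails |
| Pain only, tooth retained, bone normal | meets every listed criterion | fails |
| Mobility only, tooth retained, bone normal | meets every listed criterion | fails |
| Facial swelling only, tooth retained, bone normal | meets every listed criterion | fails |
| Abnormal periapical bone, no clinical sign | fails | not a failure |

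Four of the five rows conflict. Pain and mobility are the clearest, because facial swelling may often accompany an abscess.

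**2. Reproducing the SAP output**

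Inputs from the SAP table: N = 24, Pearson chi-square .059, minimum expected count 2.25, Fisher exact 1.000 (two-sided) and .603 (one-sided). Of all 2x2 tables with N = 24, only one fits, up to relabelling of rows and columns: 2 and 7 against 4 and 11, with margins 9/15 and 6/18.

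- Chi-square = N(ad − bc)² / (product of the four margins) = 24 × (2×11 − 7×4)² / (9×15×6×18) = 864 / 14,580 = 0.0593, p = .808.
- Minimum expected count = 9 × 6 / 24 = 2.25.
- Linear-by-linear = 0.0593 × 23/24 = 0.0568.
- Likelihood ratio = 0.0599. Continuity-corrected chi-square = 0.000. Fisher = 1.000 and .603.

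All agree with the printed figures. The output does not say which margin is the arm or which class is failure.

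**3. How few teeth move the direction**

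Assumption: the smaller outcome class is the failures. Both assignments of the margins are shown. The change considered is the removal of failures that rest only on pain, mobility or swelling.

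- Arms of 9 and 15, 6 failures: 2/9 = 22.2% against 4/15 = 26.7%. Removing one failure from the larger arm gives 22.2% against 3/15 = 20.0%, so the direction reverses.
- Arms of 6 and 18, 9 failures: 2/6 = 33.3% against 7/18 = 38.9%. Removing one from the larger arm gives 6/18 = 33.3%, a tie. Removing two gives 5/18 = 27.8%, a reversal.

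**4. Whether significance could change**

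- Arms of 9 and 15: over every removal that leaves at least one failure, the smallest p comes from 2/9 against 0/15. Chi-square = 24 × (2×15)² / (9×15×2×22) = 3.64, p = .057. Fisher = 36/276 = .13. No case reaches .05.
- Arms of 6 and 18: only the extreme case, 2/6 against 0/18, reaches it. Chi-square = 24 × (2×18)² / (6×18×2×22) = 6.55, p = .011. Fisher = 15/276 = .054. All seven failures in the larger arm would have to rest on the three unlisted signs alone. The planned 30:30 allocation also makes arms of 9 and 15 the more plausible reading.
- The reverse conflict adds failures. With arms of 9 and 15 and no removals, it takes at least five added bone failures to reach .05, and with five all must fall in the smaller arm: 7/9 against 4/15, chi-square = 24 × (7×11 − 2×4)² / (9×15×11×13) = 5.92, p = .015. The documents give no radiographic counts, so this cannot be excluded.

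**The case against.** **Scope.** The SAP defines clinical failure, while the protocol defines overall pulpotomy success. A component and a composite normally differ. This explains why the SAP has no bone criterion. It does not explain why a composite that includes a clinical examination leaves out signs that the clinical component contains.

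**An open list.** The protocol's introductory wording does not say that the list is complete, and the treatment aim mentions pain and swelling. An assessor may have applied these signs in practice. That stands as a possibility, but no written protocol rule does so. The aim describes pulpotomy in general, and swelling and mobility are otherwise only entry criteria.

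**What the SAP's rule refers to.** It directly follows the sentence on exfoliation, so its reference to the signs above could be read to include early or delayed exfoliation. That ambiguity does not remove the four signs.

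**A numerical bound.** A reader might infer that the two definitions can differ by at most 6/24 = 25% or 9/24 = 37.5%, the whole SAP failure count. The documents do not support this. If k SAP failures meet the whole protocol list and r SAP non-failures fail it on bone or tooth loss, the protocol count is 6 − k + r or 9 − k + r. Neither k nor r is reported. With 6 SAP failures, r could in principle reach 18.

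**The conclusion.** A reader might also infer that the finding of no significant difference is wrong. The working does not show that.

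**Conclusion.** The conflict holds on the text and runs in both directions. It concerns the trial's central outcome, but no printed figure is shown to be wrong because of it.

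Its size cannot be computed, because the output is unlabelled, the sign behind each failure is not given, and no radiographic results are reported. If failures are the smaller class, one tooth (arms of 9 and 15) or two teeth (arms of 6 and 18) could reverse the direction of the difference. The finding of no significant difference would probably not change. It could change only in an extreme reclassification under the less plausible margin assignment, or through radiographic failures that the documents do not report.

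**What to change.** Reconcile the protocol's success criteria with the SAP's failure rule:

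- State clinical success with one identical list in both documents, using the four SAP signs as written and without added qualifiers.
- State radiographic or overall success as a separate endpoint, using the protocol's bone and retention criteria, and add it to the SAP.
- Say in the SAP whether early or delayed exfoliation counts as clinical failure.
- Because the SAP already prints a result, disclose that the definitions differed instead of replacing one silently.
- Report failures per labelled arm under both the SAP clinical rule and the protocol list as it stands, with the number of teeth that change class in each direction.

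The cost is a wording change and a small amount of extra tabulation. The clinical signs were collected, according to the SAP. The protocol-list rate needs radiographic readings for the analysed teeth, and the SAP does not show that these are available. Where they are missing, the report should say so and give the number of teeth affected.
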